14. STATISTICAL CONSIDERATIONS

A true proportion of study subjects that are not removed from the study for toxicity or intolerance of 0.70 or higher will be considered satisfactory in this particular patient population. If the true proportion of severe toxicity -free patients is 50% or less, then Zydelig will not be considered a promising maintenance treatment post Autologous stem cell transplantation due to unacceptable toxicity.

A single-stage open-label design will be used for the study. With 34 eligible patients on the study, the Type I error or probability of declaring drug desirable if the proportion of subjects removed from study due to toxicity or intolerability is 0.50 or higher, is 0.075. The probability of rejecting the Zydelig as unacceptable due to severe toxicity compound if the proportion of subject who developed severe toxicity is less or equal to 30% rate is less than 20%. Hence, the study will have an adequate about 80% power. Addressing the safety of Zydelig, a maximum width 90% confidence interval for any grade 3 or higher toxicity will be about 32%, assuming that a total of 31 patients are enrolled. For instance, if 3 out of 31 patients (10%) develop grade 3 or higher non-hematologic toxicity, then a 90% confidence interval for the true toxicity rate is between 3% and 24%. For 31 patients in this study, if the true unknown probability of a rare toxicity is 10%, the probability of observing 1 or more toxicities is 96%, for 5% it is 80%, and if the true toxicity rate is 3% then the probability of observing one or more rare toxicities is 61%.

We plan to accrue 34 eligible patients to account for about 10% possible drop-out

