14.1 Study Design/Primary Endpoints

This single cohort open-label study will accrue 34 patients with iNHL or tiNHL. The biologically active dose of Zydelig will be 1st used at 100/150 mg PO BID. Within patient dose reductions are allowed for hematologic and non-hematologic toxicities above grade 2. The proportion of patients removed from the study due to toxicity will be reported, along with all toxicities specified by type and grade.

Early stopping guideline for toxicity: Toxicity will be monitored continuously. If it becomes evident that the proportion of patients being removed from the study for toxicity convincingly exceeds 50%, the study will be halted for a safety consultation. The toxicity stopping rule will hold enrollment.

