14.2 Sample Size/Accrual Rate

A sample size of 34 patients will be accrued and will be required to account for possible drop-out and inevaluability. The early stopping rule is defined above. Anticipated accrual is 1 patient per institution every 2 months. Therefore, accrual is anticipated to take from 20 to 36 months.

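### Section 14 attaches the error rates of a 31-patient rule (Type I error 0.075, about 80% power) to 34 patients, and states neither the pass/fail count nor the primary analysis set

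*Combined protocol and SAP*

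**What the plan says.** Section 14 treats a true proportion of 0.70 or more not removed for toxicity or intolerance as satisfactory, and 50% or less as unacceptable, in a single-stage design. The error rates are attached to 34 patients. The sentence begins "With 34 eligible patients on the study, the Type I error or probability of declaring drug desirable", and its value, for a removal proportion of one half or more, is put at 0.075. The chance of wrongly rejecting the drug when the toxicity proportion is 30% or less is put below 20%, and power at about 80%.

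The rest of the paragraph works with 31. The confidence interval width is given "assuming that a total of 31 patients are enrolled", and the rare-toxicity probabilities begin "For 31 patients in this study, if the true unknown probability of a rare toxicity is 10" per cent. The paragraph then explains the larger number: "We plan to accrue 34 eligible patients to account for about 10% possible drop-out". Section 14.2 says the 34 "will be required to account for possible drop-out and inevaluability".

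On the primary result, Section 14.1 says "The proportion of patients removed from the study due to toxicity will be reported", together with toxicities by type and grade. Nowhere do the documents give the number of removals at which Zydelig would be accepted or rejected, define inevaluable, or say how patients who leave for other reasons enter the denominator.

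**The concern.** Toxicity is the primary objective, and this is the only comparison in the trial with stated error rates. A single-stage binomial design is defined by two integers: the number analysed and the number of successes required. Section 14 names one number for the error rates and another for the rest of its calculations, and it omits the second integer altogether.

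With about 30 patients, a change of one in either integer moves the Type I error by several percentage points. The choice of denominator and count therefore decides whether the stated 0.075 and 80% apply. The trial is open-label and toxicity is watched continuously, so if the two integers are not fixed before the primary data are examined, no error rate can be claimed for the conclusion.

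**Working it through.** **Inputs (Section 14).** Unacceptable proportion not removed p0 = 0.50; satisfactory proportion p1 = 0.70; one stage; Type I error 0.075; Type II error below 0.20; n = 34 as labelled, n = 31 in the companion figures.

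**Formula.** For the rule of accepting Zydelig if at least r of n are not removed, Type I error = P(X ≥ r | n, 0.50) and power = P(X ≥ r | n, 0.70), with X binomial.

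**Step 1: the plan's figure at the plan's n = 34.**

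| Rule | Type I error | Power |
|---|---|---|
| ≥ 20 of 34 | 0.196 | 0.943 |
| ≥ 21 of 34 | 0.115 | 0.890 |
| ≥ 22 of 34 | 0.061 | 0.807 |
| ≥ 23 of 34 | 0.029 | 0.693 |

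The Type I error passes from 0.115 to 0.061, so 0.075 is not attainable. A normal approximation does not produce it either: for r = 21 and 22 it gives 0.085 and 0.043 without continuity correction, and 0.115 and 0.061 with it.

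**Step 2: n = 31.** At least 20 of 31 gives Type I error 0.0748 and power 0.808, which matches both stated figures. Over every n from 10 to 60 and every cut-off, this is the only exact rule whose Type I error rounds to 0.075.

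**Step 3: the companion figures.** The chance of at least one event is 1 − (1 − p)^n.

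| Quantity | Plan | n = 31 | n = 34 |
|---|---|---|---|
| p = 0.10 | 96% | 96.2% | 97.2% |
| p = 0.05 | 80% | 79.6% | 82.5% |
| p = 0.03 | 61% | 61.1% | 64.5% |
| Maximum exact 90% interval width | about 32% | 31.7% | 30.2% |

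These agree with 31. One figure fits less well: the exact 90% interval for 3 of 31 is 2.7% to 23.2%, against the printed 3% to 24%. The difference is small and does not affect the error rates.

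**Step 4: other analysed numbers.** This takes, for each n, the lowest cut-off with Type I error at or below 0.075.

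| n | Cut-off | Type I error | Power |
|---|---|---|---|
| 34 | 22 | 0.061 | 0.807 |
| 33 | 22 | 0.040 | 0.733 |
| 32 | 21 | 0.055 | 0.772 |
| 31 | 20 | 0.075 | 0.808 |
| 30 | 20 | 0.049 | 0.730 |
| 29 | 19 | 0.068 | 0.771 |
| 28 | 19 | 0.044 | 0.683 |

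At 27 and 26 the power is 0.728 and 0.627. Among 26 to 34, only 31 and 34 meet both limits (Type I error at or below 0.075, Type II error below 0.20).

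**Step 5: how losses count.** Suppose 3 of 34 drop out and the requirement stays at 20. If the three count as failures, the rule is 20 of the other 31 and the Type I error is 0.075. If they count as successes, it is 17 of the other 31 and the Type I error is 0.360.

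**The case against.** The strongest reply is that little follows from the label. Read 0.075 as a ceiling, and 22 of 34 satisfies everything Section 14 claims: Type I error 0.061, Type II error below 20%, power 0.807. A reader could also recover the cut-off, because only one fits the stated limits at each of the two named sample sizes. This much stands: the design is not underpowered, and the label alone would be a minor slip. But the plan gives 0.075 as the value of the error, not as an upper limit. It prints neither 20 nor 22. A cut-off that must be inferred from error rates attached to the wrong number is not a pre-specified rule.

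Second, the denominator is not wholly absent, since Section 14 speaks of eligible patients. That is fair. What is missing is the treatment of drop-outs and inevaluable patients, and Step 5 shows how much turns on it. Nor does the plan say that these choices will wait for the data; it simply does not make them beforehand.

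Third, the lower powers at 28, 29, 30, 32 and 33 come from holding 0.075 as a ceiling. Without it, 21 of 33 (0.081, 0.839) lies closer to the stated pair than 22 of 33. This also stands: the powers are conditional on the ceiling, and the sponsor may choose otherwise if it states the resulting Type I error. The row for 28 corresponds to losing 6 of 34 (18%), more than the planned 10% or so.

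Fourth, Section 14 describes the event both as removal for toxicity or intolerance and as severe toxicity. The calculation here uses removal, as do the section's opening sentence, its Type I sentence and Section 14.1. The cut-offs can be applied only once a single event is named.

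**Conclusion.** The concern holds. The stated Type I error of 0.075 cannot arise with 34 patients; it belongs to the rule of at least 20 of 31, with power 0.808. At 34 the neighbouring rules have Type I errors of 0.115 and 0.061, and carrying the implied cut-off of 20 over to 34 would give 0.196, about 2.6 times the stated value (0.196 / 0.075). The plan states neither the cut-off nor how losses enter the denominator, so the stated error rates are tied to no defined decision.

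This rests on an exact one-sided binomial test of 0.50 against 0.70, with removal for toxicity or intolerance as the event. It should be fixed, but it does not call for a larger trial.

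**What to change.** Amend Section 14 before the primary data are examined:

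1. Define the primary analysis set, for example all eligible patients who take at least one dose of Zydelig. State how patients who leave for other reasons are counted, and name one event as the primary outcome.
2. Attach Type I error 0.075 and power 0.81 to 31 analysed patients, and keep 34 as the accrual figure.
3. Print one cut-off for each analysed number. With 0.075 as a ceiling, these are the rows of the Step 4 table: at least 22 of 34, 22 of 33, 21 of 32, 20 of 31, 20 of 30, 19 of 29 and 19 of 28 not removed. For any smaller number, use the lowest cut-off with Type I error at or below 0.075.

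The cost is wording in Section 14, with no extra patients and no new data. The stated power must become about 73% to 77% if 29, 30, 32 or 33 are analysed, and about 68% if 28 are. It stays at about 81% for 31 or 34.

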14.1 Study Design/Primary Endpoints

This single cohort open-label study will accrue 34 patients with iNHL or tiNHL. The biologically active dose of Zydelig will be 1st used at 100/150 mg PO BID. Within patient dose reductions are allowed for hematologic and non-hematologic toxicities above grade 2. The proportion of patients removed from the study due to toxicity will be reported, along with all toxicities specified by type and grade.

Early stopping guideline for toxicity: Toxicity will be monitored continuously. If it becomes evident that the proportion of patients being removed from the study for toxicity convincingly exceeds 50%, the study will be halted for a safety consultation. The toxicity stopping rule will hold enrollment.

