5.3 Duration of Therapy

In the absence of treatment delays due to adverse events, treatment may continue for 1 year or 12 cycles (28 days per cycle) after transplant or until one of the following criteria applies:

- Disease Progression
- Intercurrent illness that prevents further administration of treatment
- Unacceptable adverse event(s)
- Evidence of PCP pneumonia or CMV viremia, confirmed at 2 consecutive blood draws at least 1 day apart with any value ≥ 500 IU/mL in plasma or evidence of documented CMV disease.
- Patient decides to withdraw from the study
- General or specific changes in the patient's condition render the patient unacceptable for further treatment in the judgment of the investigator.

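### The toxicity hold in Section 14.1 has no numeric boundary, event definition or counting rule, and the 0.075 Type I error in Section 14 fits 31 patients, not the 34 to which it is attached.

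*Combined protocol and SAP*

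**What the plan says.** Section 14.1 sets continuous toxicity monitoring and gives one trigger: "If it becomes evident that the proportion of patients being removed from the study for toxicity convincingly exceeds 50%, the study will be halted". The halt leads to a safety consultation. It adds: "The toxicity stopping rule will hold enrollment". Section 14.2 treats this as settled: "The early stopping rule is defined above".

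For the primary decision, Section 14 says: "A true proportion of study subjects that are not removed from the study for toxicity or intolerance of 0.70 or higher will be considered satisfactory". A true proportion of 50% or less is unacceptable. Section 14 then says "With 34 eligible patients on the study, the Type I error or probability of declaring drug desirable" at a 50% removal rate is 0.075, with power of about 80% at a 30% rate. It prints no critical count. The precision figures that follow use 31 patients, and the passage closes: "We plan to accrue 34 eligible patients to account for about 10% possible drop-out".

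Two statements bear on timing. In Section 5.3, "treatment may continue for 1 year or 12 cycles (28 days per cycle) after transplant"; in Section 14.2, "accrual is anticipated to take from 20 to 36 months".

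**The concern.** Toxicity and safety is the only primary objective, and Section 14.1 contains the only enrolment hold for toxicity in the documents. To apply it, a committee needs four things that the text does not give.

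- **A boundary.** There is no count, confidence level or minimum number of patients.
- **A denominator.** Enrolled, treated, evaluable and completed patients are all possible.
- **A rule for patients still on treatment.** Treatment can last about a year, so many outcomes are open at any look during accrual.
- **One event.** Section 14.1 counts removals for toxicity. Section 14 counts removals for toxicity or intolerance in one sentence and severe toxicity in another. Section 5.5 names only progression as a reason for removal from study, whereas 5.3 and 5.4 refer to unacceptable adverse events.

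Two committees could therefore see the same data and decide differently about holding enrolment, with nothing in the protocol to say which had followed it.

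The final test has a narrower problem. Its stated error rate does not belong to its stated sample size, so the pass mark is uncertain if more than 31 patients turn out to be evaluable.

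**Working it through.** **1. The plan's own figure.** Inputs from Section 14: unacceptable removal rate 0.50, satisfactory rate 0.30, Type I error 0.075, power about 80%, N given as 34 and as 31. Let X be the number removed among N, with success if X ≤ c. Then Type I error = P(X ≤ c | N, 0.50) and power = P(X ≤ c | N, 0.30), both exact binomial.

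| N | c | Type I error | Power |
|---|---|---|---|
| 31 | 11 | 0.0748 | 0.808 |
| 31 | 12 | 0.1405 | 0.893 |
| 32 | 11 | 0.0551 | 0.772 |
| 32 | 12 | 0.1077 | 0.867 |
| 33 | 11 | 0.0401 | 0.733 |
| 33 | 12 | 0.0814 | 0.839 |
| 34 | 11 | 0.0288 | 0.693 |
| 34 | 12 | 0.0607 | 0.807 |
| 34 | 13 | 0.1147 | 0.890 |

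The printed 0.075 and about 80% are reproduced at 31 with at most 11 removed. This agrees with the drop-out allowance: 34 × 0.9 = 30.6, about 31. At 34 no cut-off gives 0.075, and the only one within 0.075 with at least 80% power is at most 12. At 32 and 33 no cut-off meets both rates. With 34 evaluable patients and 12 removals, an analyst who carries over 11 fails the drug and one who uses 12 passes it.

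**2. Turning the verbal trigger into numbers.** The documents give no level, so this step is an assumption. Read *convincingly exceeds 50%* as an exact one-sided lower confidence bound above 0.50. For x removed among the first n, this holds when P(X ≥ x | n, 0.50) is below 1 minus the level. For example:

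- 3 of 3: 0.5³ = 0.125, below 0.20, so it is the first trigger at the 80% level.
- 4 of 4: 0.5⁴ = 0.0625, below 0.10, so it is the first trigger at the 90% level.
- 5 of 5: 0.5⁵ = 0.03125, below 0.05, so it is the first trigger at the 95% level.

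After 10 patients the triggers are 7, 8 and 9 removals at 80%, 90% and 95%; after 20 they are 13, 14 and 15.

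**3. How often each reading fires.** Assume N = 34, a look after every patient and outcomes known at once. With boundary b(n) and true rate p, the probability of k removals without having fired follows f(n, k) = (1 − p)·f(n − 1, k) + p·f(n − 1, k − 1). At each n, the mass with k ≥ b(n) moves to *fired*.

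| Level, per look | True 50% | True 30% | Power at 34 (at most 12) if every hold were permanent |
|---|---|---|---|
| 95% | 13% | 0.4% | 0.806 |
| 90% | 24% | 1.3% | 0.803 |
| 80% | 44% | 5.4% | 0.782 |

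Without a hold, power is 0.807. The level applies to each look, which is why a 95% bound checked repeatedly fires in 13% of trials, not 5%, at a true 50%.

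**4. Delay.** Removals arrive over months. With even accrual over 20 or 36 months, removals spread uniformly over 6 or 12 months after start (an assumption) and counting by enrolment order, the 95% rule fires with someone still to enrol in 10% to 13% of simulated trials at a true 50%. Delay therefore changes little at that rate, provided the counting method is fixed.

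**The case against.** The strongest reply is that Section 14.1 calls this a guideline and that it leads to a safety consultation, not to termination. Committee judgement is common in a single-arm study of this size, and the patient-level rules in Section 7 operate regardless. That is fair, and it limits the seriousness of the point. But the same paragraph calls it a stopping rule that holds enrolment, and 14.2 says it is defined. A numeric trigger for the hold leaves the consultation's judgement intact.

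Three stronger readings are tempting and should be resisted.

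- **That the final test cannot be applied at all.** A reader might infer this from the missing critical count. The count can be recovered: the error rate, the power, the precision figures and the drop-out allowance all point to at most 11 of 31. What remains is the mismatch with 34 and the silence on 32 to 34 evaluable.
- **That the hold could fire in anything from 13% to 74% of trials at a true 50%.** The upper figure takes any raw share above 50% from patient 10. Six removals in 10 is hard to call convincing, and the wording asks for more than a bare majority. The fairer span is 13% to 44%. At a true 30% the readings differ much less, 0.4% to 5.4%.
- **That no threshold exists anywhere.** Section 9.6 refers to a monitoring plan in an outside handbook and Section 13 to a monitoring procedure. Neither was available. One may contain a working threshold, but the protocol cites none.

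**Conclusion.** The point stands for Section 14.1: the only enrolment hold for toxicity has no stated boundary, denominator, counting rule or single event. Across reasonable confidence levels, its chance of firing at a rate that the plan calls unacceptable varies about threefold (13% to 44%). These figures assume an exact lower bound, a look after each of 34 patients and immediate outcomes. They show the spread between readings and do not identify what the sponsor intended.

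For Section 14 the conclusion is narrower. The 0.075 belongs to at most 11 of 31, not to 34, and the critical count should be printed. The trial can run as written, but the hold cannot be audited against the protocol, and the final decision is ambiguous if 32 to 34 patients are evaluable. It should be corrected.

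**What to change.** **Section 14.** State the evaluable denominator and print the critical count with its exact Type I error and power:

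- 31 evaluable: at most 11 (0.075 / 0.808)
- 32: at most 11 (0.055 / 0.772) or at most 12 (0.108 / 0.867)
- 33: at most 11 (0.040 / 0.733) or at most 12 (0.081 / 0.839)
- 34: at most 12 (0.061 / 0.807)

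At 32 and 33 the sponsor must choose in advance which rate gives way.

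**Section 14.1.** Use the same counted event as the primary test and reconcile it with Sections 14 and 5.5. Replace the verbal trigger with a numeric boundary for the hold and consultation. Count by order of enrolment with every treated patient in the denominator, and say that patients who leave for progression or other reasons stay in it as non-events. A row is met once that many of the first n are removed, even if others among them are still on treatment.

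An example at the 95% level: 5 of the first 5, 7 of 8, 9 of 11, 10 of 13, 12 of 16, 13 of 18, 15 of 21, 16 of 23, 18 of 26, 19 of 28, 20 of 30 or 22 of 33. These twelve rows reproduce the every-patient rule exactly up to patient 34. The level is the sponsor's choice. If a threshold already exists in the handbook or monitoring procedure, cite it here.

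**Cost.** Two short tables in an amendment, with the usual IRB submission. Even if every hold were permanent, power at 34 goes from 0.807 to 0.806 (95%), 0.803 (90%) or 0.782 (80%).

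### The Section 14.1 enrolment hold is not linked to the primary decision rule, so the plan lets accrual continue after the removal count has made acceptance impossible

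*Combined protocol and SAP*

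**What the plan says.** Section 14 calls the treatment satisfactory at "A true proportion of study subjects that are not removed from the study for toxicity or intolerance of 0.70 or higher", and not promising "If the true proportion of severe toxicity -free patients is 50% or less". For 34 eligible patients in a single stage, it states that the "probability of declaring drug desirable if the proportion of subjects removed from study due to toxicity or intolerability is 0.50 or higher, is 0.075", and concludes: "Hence, the study will have an adequate about 80% power". It prints no number of removals at which the treatment is accepted or rejected.

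Two sample sizes appear. The plan says "We plan to accrue 34 eligible patients to account for about 10% possible drop-out", while the precision statements are made "assuming that a total of 31 patients are enrolled".

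Section 14.1 adds an early stopping guideline under continuous monitoring: when the "proportion of patients being removed from the study for toxicity convincingly exceeds 50%, the study will be halted for a safety consultation". It then says that this rule holds enrolment. Section 14.2 only refers back to it. Section 9.6 places the trial under a monitoring committee but gives no threshold.

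**The concern.** The primary test and the enrolment hold use nearly the same event, but they are set at different levels and neither refers to the other. The test must reject well below 50% removed, because it has to separate 50% from 30%. The hold waits for a share convincingly above 50%. Removals only accumulate, so there is a count after which the treatment can no longer be accepted, and nothing in the plan pauses accrual at that count.

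The events also differ slightly: the test counts removal for toxicity or intolerance, while the hold names toxicity only, which makes the hold harder to reach. At stake is the exposure of further patients to a regimen that has already missed the trial's own tolerability criterion, without a planned pause to ask whether that is still justified.

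**Working it through.** **Inputs.** From Section 14: unacceptable removal rate 0.50 (1 − 0.50 not removed), satisfactory removal rate 0.30 (1 − 0.70), type I error 0.075, power about 80%, 34 accrued, 31 after about 10% drop-out (34 × 0.9 = 30.6). From 14.2: accrual over 20 to 36 months. From 5.3: treatment for up to 12 cycles of 28 days (336 days).

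**Step 1: recover the acceptance count.** Accept if removals X ≤ c. Type I error = P(X ≤ c | n, 0.50); power = P(X ≤ c | n, 0.30), exact binomial.

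| n | accept if X ≤ | type I error | power |
|---|---|---|---|
| 31 | 11 | 0.0748 | 0.808 |
| 34 | 12 | 0.061 | 0.807 |
| 34 | 13 | 0.115 | 0.890 |

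Both stated figures are reproduced by 11 of 31. No count on 34 gives 0.075.

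**Step 2: failing count.** Acceptance becomes impossible at removal 12 of 31 (12/31 = 38.7%) or 13 of 34 (13/34 = 38.2%). These are shares of the planned final number, not running rates: 4 removed among the first 10 (40%) settles nothing.

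**Step 3: can the guideline act at that moment?** Take the share over patients enrolled so far.

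- 31-patient rule: 12/23 = 52.2%, 12/24 = 50.0%, 12/30 = 40.0%. With 24–30 enrolled the share does not exceed 50%.
- 34-patient rule: 13/25 = 52.0%, 13/26 = 50.0%, 13/33 = 39.4%. With 26–33 enrolled the share does not exceed 50%.

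In those ranges no meaning of *convincingly* lets the guideline act when failure occurs; it could act only later, if removals go on mounting. For smaller numbers enrolled the meaning matters. Suppose it is an exact one-sided test, P(X ≥ x | n, 0.50) ≤ a. At a = 0.05, 12 removals trigger the hold only with 16 or fewer enrolled. Thirteen removals trigger it with at most 18 enrolled (a = 0.05), 19 (a = 0.10) or 21 (a = 0.20). At full accrual, a = 0.05 needs 21 of 31 or 23 of 34.

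**Step 4: size.** Simulation with 31 patients, even accrual over 20 or 36 months, and the one-sided 95% reading. The delay to removal is not in the documents and is assumed. Mean number enrolled, hold at the 12th removal against the 50% guideline:

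| delay to removal | true rate 50% | true rate 60% |
|---|---|---|
| none | 24 v 28–29 | 20 v 24–25 |
| exponential, mean 3 months | 26–27 v 30–31 | 22–24 v 28–30 |
| even over 336 days | 27–30 v 31 | 24–28 v 30–31 |

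At a true rate of 50% the test fails in 1 − 0.0748 = 92.5% of trials, while the guideline so read holds enrolment before full accrual in 0–14%.

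**Step 5: looser readings.** With no delay and a true rate of 50%, a one-sided 80% bound stops at a mean of 22, and a raw share above 50% from patient 10 at 18, against 24 for the failing count. At 60% these are 15 and 13, against 20. With a mean 3-month delay, 36-month accrual and a true rate of 60%, the 80% bound and the failing count both stop at 22. With faster accrual or later removals the failing count is usually reached first.

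**The case against.** The strongest reply is that this is a declared single-stage design, which need not stop for futility. The guideline in 14.1 is a safety rule placed at the plan's own unacceptable rate, and accrual is supervised through continuous monitoring and committee review of serious events. That is fair: no rule of design is broken, and the point is an improvement.

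Secondly, the failing count is inferred. It moves with the evaluable number: 12 or fewer of 33 gives 0.081 and 0.839, and with 32 neither 11 (0.055, 0.77) nor 12 (0.108, 0.87) fits well. This stands, and is why printing the rule comes first.

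A reader might infer more than the documents support:

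- *That the hold sits above the failure limit however it is read.* Early in accrual the 50% guideline can act first. Twelve of 20 (60%) already exceeds 50% as a raw share and escapes only a strict bound.
- *That further enrolment has no value for the primary question.* The primary objective is to determine toxicity and safety, and Section 14 supports 31 patients partly by interval width and by the chance of seeing rare toxicities.
- *That patients will certainly be enrolled after failure.* The plan permits it; whether and how many depends on quantities that are not known.

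**Conclusion.** The concern holds in limited form. The plan's figures imply that the 12th removal of 31 (or 13th of 34) ends any chance of acceptance. If it falls late in accrual, the only enrolment hold cannot act at that point.

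The size is uncertain. At a true rate of 50%, 31 patients and a one-sided 95% reading, mean enrolment is about 24–30 with a hold at the failing count and 28–31 without. Under looser readings the gain shrinks. Across the readings, rates and delays simulated, the failing count came before the 50% guideline in about 6% to 95% of trials.

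The result rests on the inferred acceptance count, on a running share taken over patients enrolled so far, and on the assumed delays and even accrual.

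**What to change.** In Section 14, print the acceptance count and the evaluable number to which it applies, and say how the count changes if the evaluable number differs.

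In Section 14.1, add that enrolment is also held for the same safety consultation once removals for toxicity or intolerance reach the first count at which acceptance under Section 14 is no longer possible (the 12th for the 31-patient rule, the 13th if the rule is written on 34). Keep the 50% guideline beside it. Which final rule to print is for the study team.

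The cost is a few lines of text, and the count is already monitored. Type I error and power do not change, because the added hold acts only in trials whose verdict is already fixed. It is a pause for consultation, so accrual may resume.

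If the hold becomes permanent, precision is lost. At 24 patients instead of 31, the maximum exact 90% interval width is about 36% instead of 32%. The chance of seeing a 5% toxicity is 1 − 0.95^24 = 71% instead of 1 − 0.95^31 = 80%. PFS, OS and NRM would also rest on somewhat fewer patients.
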